8. BENEFITS

Participants have a good chance of improvement in their mood symptoms as versions of this new type of rTMS treatment has already demonstrated consistent efficacy.

9. PRIVACY AND CONFIDENTIALITY

All participant information and specimens are handled in compliance with the Health Insurance Portability and Accountability Act (HIPAA) and privacy policies of Stanford University, Stanford Health Care, and Stanford Children's Health.

9. STATISTICAL CONSIDERATIONS

Primary Mechanistic Objective and Relevant Clinical Objective

Primary Mechanistic Objective: To determine if accelerated theta-burst stimulation can provide a rapid reduction in acute depressive symptoms in treatment resistant outpatients with MDD. **In other words, the Primary Outcome Measure** is the change in depressive mood.

Relevant Clinical Objective: To determine the effect of active, accelerated theta-burst stimulation over the left DLPFC on decreasing depressive symptoms as measured by a change in the *Montgomery-Asberg Depression Rating Scale (MADRS)*.

Relevant Clinical Hypothesis: Active accelerated theta-burst stimulation over the left DLPFC will significantly reduce depressive symptoms in treatment resistant outpatients with MDD.

Secondary Objectives

Secondary Objective A: To explore whether accelerated theta-burst stimulation over the left DLPFC results in functional connectivity changes between the subgenual anterior cingulate cortex (sgACC) and Default Mode Network (DMN) using functional magnetic resonance imaging (fMRI).

Secondary Hypothesis A: Active accelerated intermittent theta-burst stimulation over the left DLPFC will result in functional connectivity changes between the sgACC and the DMN.

Secondary Objective B: To explore whether accelerated intermittent theta-burst stimulation over the left DLPFC leads to changes in depression symptoms as assessed by the Hamilton Depression Rating Scale 17-item (HAM-17) and Hamilton Depression Rating Scale 6-item (HAM-6).

Secondary Hypothesis B: Active accelerated intermittent theta-burst stimulation over the left DLPFC will lead to decreased scores on the HAM-17 and HAM-6 compared to baseline, indicating decreased depression symptomatology.

General Design Issues

Statistical Hypotheses: We will examine the effect of active aiTBS on the functional connectivity between sgACC and DMN. In the *Relevant Clinical Hypothesis*, we will examine the effect of active aiTBS on reducing depressive symptoms in treatment resistant outpatients with MDD as assessed by the MADRS. In *Secondary Hypothesis B*, we will also examine the effect of active aiTBS on reducing depressive symptoms as measured by the HAM-17 and HAM-6.

Rationale for Study Design: The design will allow to assess the feasibility of modulating the neural circuitry underlying depression with accelerated intermittent theta-burst stimulation (aiTBS) alongwith the measuring the effects of this neuromodulation strategy on the underlying neural circuitry. The same subjects are utilized for all three MRI scan sessions, that is, for the pre-aiTBS scan session, the immediate post-aiTBS scan session and for the 1-month post-aiTBS follow-up scansession (to address functional connectivity aims). The rationale for using the same subject threetimes is to enable analysis of functional connectivity differences in the left DLPFC and dACC in response to aiTBS across time.

Sample Size

The study will be powered for an estimated effect size of Cohen's $d=0.6$ for change in Montgomery-Åsberg Depression Rating Scale (MADRS) between baseline and one month post treatment using within subject t-test. Prior investigations of iTBS of the L-DLPFC for treatment resistant depression reported an effect size of $d=1.337$, leaving our estimate conservative. We will set the probability of rejecting a true null hypothesis (Type 1 error, alpha) at 0.05 (two-sided) with 80% power. That will require a final sample size of 23 participants. This study will aim to recruit 30 individuals assuming approximately 20% missing data due to unusable imaging data or dropouts.

Interim Analyses and Stopping Rules

Because of the anticipated low level of adverse events of aiTBS and MRI, interim analysis of data,protocol and adverse events will occur by study staff at least once a year. Serious adverse events will be reviewed on a monthly basis, unless a more urgent review is requested. Only under extreme circumstances or if it were determined that a high level of side effects was due to aiTBS and/or MRI, would the PI be charged with breaking the study mask. This study will be stopped prior to its completion if: [1] the intervention is associated with adverse effects that call into question the safety of the intervention; [2] difficulty in study recruitment or retention will significantly impact the ability to evaluate the study endpoints; [3] any new information becomes available during the trial that necessitates stopping the study; or [4] other situations occur that might warrant stopping the study.

Data Analyses

The Primary Mechanistic Outcome Measure for this study is percent change in MADRS scoreat one-month post treatment. **The Relevant Clinical Outcome Measure** is a reduction in depressive symptoms in treatment resistant outpatients diagnosed with MDD, as measured

by change in MADRS score. For secondary aims, the emphasis is on identifying the magnitude of effects (clinical significance, effect size) instead of statistical significance. Following the convention in imaging studies, we will conduct our primary analyses treating the contrast (baseline versus post) as one univariate outcome. We do not expect much variation across our narrowly defined subjects, although some variation is still possible. Given that, we will also analyze the data in the linear mixed effects modeling framework allowing for random intercepts (although this is not customary in imaging studies) as a way of sensitivity analysis.

Moderator/mediator investigation: We will explore various baseline variables as potential moderators of aiTBS. For this investigation, we will employ the MacArthur approach for moderator analysis. We will also examine potential mediators of rTMS effect using the MacArthur approach as well as contemporary causal mediation approaches, which we believe will provide valuable insights regarding the neuromodulation mechanism for the next phase of investigation.

Handling of missing data: As a way of assessing the impact of missing scan sessions, we will repeat our main analyses treating outcomes measured in the pre-aiTBS scan and in the 1-month post-aiTBS scan as multivariate outcomes. This will allow us to include all participants in the analysis as long as two of the three scans are available. In this analysis framework, missing data will be handled assuming that it is missing at random conditional on observed scan session data (maximum likelihood estimation). Analyzing the data using both univariate and multivariate analysis approaches will also serve as sensitivity analyses. Additionally, we will include the order of scan sessions in the model to account for the carryover and order effects.

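### The SAP's sample size inputs require 24 evaluable participants for 80% power, not the stated 23 (78.5%); recruitment of 30 is unaffected

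*SAP*

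**What the plan says.** The Sample Size paragraph of SAP section 9 bases the calculation on "an estimated effect size of Cohen's $d=0.6$ for change" in MADRS, measured "between baseline and one month post treatment using within subject t-test". The error rate and power are given as "Type 1 error, alpha) at 0.05 (two-sided) with 80% power". The result follows directly: "That will require a final sample size of 23 participants". Recruitment is then set: "This study will aim to recruit 30 individuals assuming approximately 20% missing data due to unusable imaging data or dropouts".

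The same paragraph calls 0.6 conservative against an effect of 1.337 reported in earlier work. The protocol gives the same enrolment of 30, in Study Procedures (section 2a) and Planned Enrollment (section 6a), and describes a single group. Neither document names the sample size formula or software, and neither gives a standard deviation or a correlation between baseline and follow-up scores.

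**The concern.** The SAP names its test, sidedness, alpha, power and effect size, so the required number can be recomputed. The figure that comes out is 24, and 23 falls just short of the stated power. A required sample size is a minimum and is rounded up, so a number that misses the target is wrong as stated, even if only slightly.

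What is at stake is the accuracy of the planning statement. The figure of 23 is the number of evaluable participants that the SAP presents as sufficient. A reader who uses it to judge whether the completed trial kept its planned power would be off by one participant.

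**Working it through.** **Inputs, all from the SAP's Sample Size paragraph:** d = 0.6; within-subject t-test; alpha 0.05 two-sided; power 80%; stated final sample 23; recruitment 30; loss about 20%.

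**Assumption:** d is the standardised mean change (mean change divided by the SD of the change), the natural reading for a within-subject t-test.

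**Step 1. Try to reproduce 23.**

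- Normal approximation: n = ((1.960 + 0.842)/0.6)² = 7.849/0.36 = 21.80, so 22.
- Normal approximation plus the usual small-sample term: 21.80 + 1.960²/2 = 21.80 + 1.92 = 23.72, so 24. Rounding this down gives 23.
- One-sided exact t-test: 19 participants give 80.8%, so a change of sidedness does not explain 23.

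Of these routes, only truncating 23.72 leads to 23. That is a plausible origin, but the documents do not confirm it.

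**Step 2. Exact power for the named test.** Power = P(|T| > t₀.₉₇₅,ₙ₋₁), where T has a noncentral t distribution with n − 1 degrees of freedom and noncentrality 0.6√n.

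| n | Critical t | Noncentrality 0.6√n | Power |
|---|---|---|---|
| 22 | 2.080 | 2.814 | 76.5% |
| 23 | 2.074 | 2.877 | 78.5% |
| 24 | 2.069 | 2.939 | 80.4% |

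The smallest n with at least 80% power is 24. At 23 the shortfall is 80.0 − 78.5 = 1.5 percentage points. Put the other way, 23 participants give exactly 80% power for d = 0.611.

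**Step 3. Recruitment.**

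- From 24: 24/0.80 = 30.0, the number planned.
- From 23: 23/0.80 = 28.75, so 29.
- From 30 recruits: 30 × 0.80 = 24 evaluable, with 80.4% power.

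The recruitment figure therefore already matches the corrected requirement.

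**Step 4. Dependence on the reading of d.** If d were instead scaled to a raw-score SD that is equal at both visits, the standardised change would be 0.6/√(2(1 − r)), where r is the baseline to follow-up correlation. The documents give no r, so the values below are illustrative.

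| r | Standardised change | Exact n for 80% power |
|---|---|---|
| 0.3 | 0.507 | 33 |
| 0.4 | 0.548 | 29 |
| 0.5 | 0.600 | 24 |
| 0.6 | 0.671 | 20 |
| 0.7 | 0.775 | 16 |

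Under that reading 23 would need r of about 0.52 (1 − (0.6/0.611)²/2). Nothing in the documents suggests that such a value was used.

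**The case against.** The strongest reply is that the gap is within ordinary calculation tolerance. The SAP names the test but not the formula. The stated 23 lies between the normal approximation (22) and the exact result (24), and on the normal approximation 23 gives 82.1% power. The effect size is a planning guess to one decimal place, and moving it from 0.600 to 0.611 would make 23 correct. At the cited 1.337, power at 23 exceeds 99.9%. No conduct or analysis decision turns on the figure.

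All of this stands as an argument about size. It does not make 23 right: the normal approximation belongs to a z-test, the SAP specifies a t-test, and the smallest number that meets the stated target under that test is 24.

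A reader might go further and infer that the loss allowance has no room left, that the trial can tolerate at most six losses, or that 30 is too few. The documents do not support this. An allowance exists to absorb the loss it plans for, and 30 absorbs the stated 20% in full. The 20% also covers unusable imaging, and an unusable scan does not by itself remove a MADRS score. Losses on the powered endpoint may therefore be below 20%; the SAP gives no split.

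**Conclusion.** The stated final sample size is wrong by one. On the SAP's own inputs, with d read as the standardised mean change, 80% power needs 24 evaluable participants (80.4%); 23 gives 78.5%. This is a minor error of one participant and 1.5 power points.

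It should not be read as showing an underpowered trial, since planned recruitment of 30 delivers 24 at the stated loss. Nor should it be read as setting up a false claim of success for a trial that finishes with exactly 23. Neither document makes 23 a stopping threshold or a condition for analysis, and the final estimate, interval and test would be the same whichever figure is printed.

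The conclusion rests on the reading of d. Under another scaling the required number depends on a correlation that the SAP does not give.

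**What to change.** In the Sample Size paragraph of SAP section 9, replace 23 with 24 and add that 24/0.80 = 30. Alternatively, keep 23 and state the power as about 78.5%. The first is preferable because the power, loss allowance and recruitment figures then agree. It would help to say in the same sentence that d is the mean change divided by the SD of the change, and that the noncentral t distribution was used.

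Do not add a statement that at most six losses are tolerated, because it would count every unusable scan as a lost MADRS value.

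Cost: one figure and a short clause in the SAP. No change to recruitment and no extra participants.

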2. STUDY PROCEDURES

a. Procedures

We will recruit a total of 30 participants.

All participants will receive intermittent theta burst (iTBS) over L DLPFC (five days 10x/day).

Participants will have moderately treatment resistant major depressive disorder as defined by a score of ≥ 20 on the HAMD-17, MADRS and BDI-II scales.

Screening Time-Period:

Patients will undergo a screening time period where their eligibility will be confirmed. This may occur any time prior to the baseline time period. Following screening informed consent, clinical interviews and behavioral testing will occur at the Stanford Psychiatry

department. The clinical interview will include a screen for inclusion and exclusion criteria, MRI safety, TASS, medical and psychiatric history, neurological exam, urine tox screen, pregnancy test, and motor threshold (see Motor Threshold section for details below).

Diagnosis will be confirmed with the MINI and/or SCID. We will also request medical records to confirm information collected during the screening visit. Patients will be staged using the Maudsley staging method and a trained rater will perform: HAMD-21, MADRS, ATHF, YMRS and SSI.

Patients will fill out self-reports including the BDI-II and C- SSRS.

Baseline Time-Period:

Baseline visits will be separate from screening visits to confirm stability of symptoms (stability is defined as a difference in MADRS score below 30% from screening).

Participants will have an MRI scan in the morning.

Baseline clinical measures (MADRS and HAMD-17) will be performed. In addition, patients will fill out the C-SSRS self-report.

Participants will practice using the heart rate monitor that they will be using for the remainder of the study.

Active Study Time-Period:

iTBS sessions will be scheduled in a 5-day sequence, resulting in a total of 50 sessions over 5 days. Participants will receive 10 daily stimulations. Each session is separated by a 50-minute break. This separation between sessions decreases the risk of associated TMS side effects (e.g. irritation from the device, headache).

Follow-up Time-Period:

Patients will have the same clinical assessments as well as MRI scans that were completed during the baseline time-period at the immediate post-treatment and 1-month post-treatment mark. Heart rate will be measured during these time points.

Motor threshold:

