The subjects will undergo an MRI scan of the brain that will require about 1 hour in the MRI scanner. A structural MRI scan and an fMRI scan will be done using a 3T system at Stanford facilities.

During the scan, subjects will lie on the table in the magnet for 1 hour while the images are acquired. Instructions may be given through an auditory system. Subjects will wear earplugs and may be fitted for a bite bar to help them to keep their head still during the scans; for studies that enroll older adults, a bite bar will not be used so as to accommodate participants with dentures. These procedures have been used previously in younger and older adults alike, and do not cause undue distress in subjects. Brain images will be made using conventional MRI imaging (including functional and diffusion tensor

imaging).

Patients will undergo a minimum of 3 scans up to a maximum of 6 scans, each 1 hour in length.

Acquisition and data extraction:

Clinical interview ratings will be made by trained study personnel. Individual item scores will be recorded and then summed according to symptom cluster and scale definitions.

Outcome measures:

The primary outcome measure for this study will be change in MADRS score. The MADRS is a clinical assessment tool used to rate a patient's level of depression and is the standard scale used for depression research studies.

Secondary measures will include functional connectivity change of the sgACC to the DMN. Primary outcome will be assessed as the change between baseline and immediate post-stimulation, with secondary measures to include the change between baseline and immediate post- stimulation and 1-month post-stimulation.

Other secondary measures include clinical interview assessments, to be performed according to the timeline above, include:

HAMD-17 (Hamilton Depression Rating Scale 17-Item)
C-SSRS (Columbia Suicide Severity Rating Scale)
HAMD-6 (Hamilton Depression Rating Scale 6-Item)
MADRS (Montgomery-Asberg Depression Rating Scale)

b. Procedure Risks

These methods are the least risky because the intervals of stimulation have been shown to be appropriate for theta burst stimulation in the motor system with no adverse outcomes.

We don't anticipate any risk from the procedures themselves, aside from those mentioned in section 7a i.

c. Use of Deception in the Study

NA

d. Use of Audio and Video Recordings

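### The protocol puts the primary MADRS endpoint at immediate post-stimulation, while the SAP defines and powers it at one month, and nothing says which governs

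*SAP*

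**What the plan says.** **Protocol, section 2a, Outcome measures.** The primary variable is change in MADRS, and its timing is given as: "Primary outcome will be assessed as the change between baseline and immediate post-stimulation". The sentence continues "with secondary measures to include the change between baseline and immediate post- stimulation and 1-month post-stimulation". A separate list of further secondary measures in the same section again includes MADRS.

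**SAP, section 9, Data Analyses.** "The Primary Mechanistic Outcome Measure for this study is percent change in MADRS scoreat one-month post treatment". The same paragraph adds a second MADRS outcome, the relevant clinical one, as change with no visit attached. The primary analysis is then described as "treating the contrast (baseline versus post) as one univariate outcome", without naming the post visit.

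**SAP, section 9, Sample Size.** Power is computed for d = 0.6 in MADRS change "between baseline and one month post treatment using within subject t-test", at two-sided alpha 0.05 and 80% power. This gives 23 participants, raised to 30 "assuming approximately 20% missing data due to unusable imaging data or dropouts".

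**SAP, section 9, primary objective.** "To determine if accelerated theta-burst stimulation can provide a rapid reduction in acute depressive symptoms". No visit is given.

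**Timing of the visits.** Protocol 2a (Imaging and Biomarkers) puts the immediate scan 1 to 3 days after the last stimulation and the one-month scan at 25 to 30 days. Clinical assessments are repeated "at the immediate post-treatment and 1-month post-treatment mark".

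**The concern.** This is a single-arm study whose confirmatory claim rests on one within-subject test of MADRS. The two documents apply that test at visits about four weeks apart. A team following both would produce two primary results.

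Three things are at stake:

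- **Which result decides.** If one visit gives p < 0.05 and the other does not, the trial is positive under one document and negative under the other.
- **Error control.** The stated 5% type I error assumes one pre-specified test. It no longer holds if the visit can be chosen after the results are seen.
- **Power.** The sample-size statement supports the SAP's endpoint only.

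A lesser problem is the metric. The SAP's primary outcome is percent change, while its own sample-size text and the protocol speak only of change.

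**Working it through.** **1. The definitions side by side**

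| Source | Metric | Visit | Status |
|---|---|---|---|
| Protocol 2a, Outcome measures | change | immediate post-stimulation | primary |
| SAP 9, Data Analyses | percent change | one month | primary (mechanistic) |
| SAP 9, Data Analyses | change | none given | relevant clinical outcome |
| SAP 9, Sample Size | change | one month | basis for power |
| SAP 9, primary objective | reduction in symptoms | none given | primary |

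No available section sets an order of precedence.

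**2. The plan's own sample size**

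Inputs from SAP 9, Sample Size: d = 0.6, two-sided alpha 0.05, power 80%, about 20% loss.

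- Normal approximation: n = ((1.960 + 0.842)/0.6)² = 21.8, so 22.
- Exact noncentral t, with noncentrality d√n and n − 1 degrees of freedom: power is 0.785 at n = 23, 0.804 at n = 24 and 0.888 at n = 30. The exact requirement is 24.
- Allowance for loss: 23/0.8 = 28.75, so 29; 24/0.8 = 30.

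The stated 23 and 30 are reproduced to within one participant. The arithmetic is sound for the one-month endpoint.

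**3. Power for the protocol's endpoint**

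The documents give no effect size specific to the immediate visit. Over an assumed range, using the exact t-test:

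| d | Power at n = 23 | n for 80% power |
|---|---|---|
| 0.4 | 0.45 | 52 |
| 0.5 | 0.63 | 34 |
| 0.6 | 0.79 | 24 |
| 0.7 | 0.89 | 19 |
| 0.8 | 0.96 | 15 |

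If d = 0.6 is also assumed at the immediate visit, the required n does not change.

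**4. How often the two visits would disagree**

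Assumptions not in the documents: bivariate normal change scores, the same d at both visits, and correlation rho between the two change scores of 0.5, 0.7 or 0.9. The number with MADRS data is taken as 23 to 30, because part of the 20% allowance is for unusable imaging, which need not remove a MADRS score. Each visit is tested by a two-sided one-sample t-test at 0.05, with 200,000 simulated trials per cell. The table shows the probability that exactly one visit is significant:

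| d | n | rho 0.5 | rho 0.7 | rho 0.9 |
|---|---|---|---|---|
| 0.6 | 23 | 0.241 | 0.189 | 0.109 |
| 0.6 | 30 | 0.149 | 0.119 | 0.069 |
| 0.8 | 23 | 0.070 | 0.056 | 0.034 |
| 0.8 | 30 | 0.020 | 0.018 | 0.011 |
| 1.0 | 23 | 0.008 | 0.007 | 0.005 |
| 1.0 | 30 | <0.001 | <0.001 | <0.001 |

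At d = 1.337, the prior value the SAP cites, power exceeds 0.999 and disagreement is about 0.

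**5. Unequal effects**

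If d were 1.337 at one visit and 0.6 at the other, the first test would almost always succeed. Disagreement is then one minus the power at d = 0.6: 1 − 0.785 = 0.215 at n = 23 and 1 − 0.888 = 0.112 at n = 30.

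**6. Type I error if either visit can count**

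Under independence the chance of at least one p < 0.05 is 1 − 0.95² = 0.0975. Simulated under no true change, it is 0.091, 0.084 and 0.071 for rho = 0.5, 0.7 and 0.9, the same at n = 23 and n = 30.

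**The case against.** The strongest replies are these.

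- **The protocol's secondary clause is ambiguous.** It follows a sentence about functional connectivity and repeats the immediate visit, so it may give visits for connectivity rather than MADRS. That is a fair reading, but it does not remove the conflict. The protocol's primary visit is still immediate post-stimulation, one month is nowhere its primary, and MADRS also appears in the protocol's further list of secondary measures.
- **The SAP is largely consistent with itself.** Wherever it attaches a visit to a primary or main analysis, that visit is one month, including the missing-data paragraph, although that paragraph concerns scans. This stands: the conflict is chiefly between the two documents. The objective's wording and the unnamed post visit simply fail to settle it.
- **With a large effect the issue is small.** Under equal effects, disagreement is at most 7% at d = 0.8 and below 1% at d = 1.0, and the SAP calls 0.6 conservative. This also stands, but only if the effect is similar at both visits, which the documents do not establish. Step 5 of the working shows what happens otherwise. Even when both tests succeed, the headline estimate can differ by visit.
- **The sample size is not shown to be wrong.** Correct. What is missing is a justification for the protocol's endpoint; a power deficit has not been demonstrated.

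**Conclusion.** The concern holds. The operative text of the two documents gives the primary MADRS endpoint two different visits, and the power statement is tied to only one of them. This must be resolved before outcome data are analysed, because afterwards the choice could be influenced by the results.

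The practical size depends on the true effect. The conflict matters most near the SAP's planning value of 0.6, where roughly one trial in four to one in fourteen would give conflicting answers across the assumed correlations and n = 23 to 30. It matters little if the effect is near 1.337 at both visits. These percentages are illustrations resting on the assumptions in step 4 of the working; the contradiction itself rests on none of them. The judgement is limited to the text available for review, from which some pages were removed.

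**What to change.** Put one identical sentence in protocol 2a (Outcome measures) and SAP 9 (Data Analyses), for example:

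> The single primary endpoint is [change in points | percent change] in MADRS total score from baseline to [immediate post-treatment | one month], tested by a two-sided within-subject t-test at 0.05.

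If percent change is chosen, state that the test is a one-sample t-test of each participant's percent change against zero. The choice of visit and metric is the sponsor's.

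Then:

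- List the other visit and the other metric as named secondary endpoints, and state where the SAP's relevant clinical outcome falls.
- Tie the Sample Size sentence to the chosen endpoint. If that is not one-month change, say that d = 0.6 is an assumption for it and justify it.
- Define the baseline-versus-post contrast separately for MADRS and for imaging. Keep the scan-session missing-data analysis on the one-month scan that the SAP already names.

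The cost is wording in the protocol, the SAP or both, and possibly an effect-size justification. No visits are added, because the clinical assessments are already planned at both time points.

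### With one arm and one fixed scan sequence, the SAP's moderator and mediator analyses give predictors and correlates of change, and its scan-order term cannot separate carryover from time

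*SAP*

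**What the plan says.** Protocol section 2a describes one treatment for everyone: "All participants will receive intermittent theta burst (iTBS) over L DLPFC (five days 10x/day". Section 6a recruits all 30 participants to that regimen. Scans are taken before treatment, 1 to 3 days after the last stimulation, and 25 to 30 days after it (Protocol 2a, Imaging and Biomarkers). SAP section 9, Rationale for Study Design, uses the same participants at all three sessions.

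Against that design, SAP section 9 (Data Analyses) plans three things:

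- **Moderators.** "We will explore various baseline variables as potential moderators of aiTBS", followed by "For this investigation, we will employ the MacArthur approach for moderator analysis". No variable is named.
- **Mediators.** "We will also examine potential mediators of rTMS effect using the MacArthur approach as well as contemporary causal mediation approaches". No mediator is named. The results are meant to inform thinking about mechanism in the next phase of work.
- **Scan order.** Under Handling of missing data, the main analyses are repeated with the pre-treatment and one-month scans as multivariate outcomes, including participants "as long as two of the three scans are available". Then: "we will include the order of scan sessions in the model to account for the carryover and order effects".

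The only identifying assumption in these paragraphs is that missing scan data are missing at random.

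**The concern.** Moderation means that the effect of treatment differs by a baseline variable. Mediation means that treatment changes an intermediate variable, which in turn changes the outcome. Both are defined by comparison with what would have happened without treatment, and this trial does not observe that. It can be assumed, but the SAP does not say so. A purely prognostic factor could therefore be carried into the next study as a moderator, and a correlation between two changes could be carried forward as a mechanism.

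The scan-order term raises a separate problem. Adjusting for order and carryover makes sense when sequences differ between participants. Here the schedule gives everyone the same sequence, so the model would appear to make an adjustment for which the design holds no information.

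**Working it through.** The plan gives no figure for these analyses, so there is none to reproduce. The check is whether each quantity can be estimated from the planned design, using the rank of the design matrix for 30 participants. No effect size is needed for that.

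**Moderation.** Let x be a baseline variable, u the slope of untreated change on x, and m the moderation of the treatment effect by x. Then

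change = (a + u·x) + (t + m·x) + error = (a + t) + (u + m)·x + error.

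The fitted slope is b = u + m.

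| Model columns | Rank |
|---|---|
| 1, time, x, time·x (pre and one month) | 4 of 4 |
| the same plus treated, treated·x (treated = 1 after aiTBS) | 4 of 6 |
| three visits: 1, v1, v2, x, v1·x, v2·x, treated, treated·x | 6 of 8 |
| between participants: 1, T, x, T·x with T = 1 for all | 2 of 4 |

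The association with change is estimable, but its split into u and m is not. If u is 0, b or 2b, then m is b, 0 or −b, with identical data. For example, a total slope of 0.4 split as 0 + 0.4, 0.2 + 0.2, 0.4 + 0 or 0.6 − 0.2 gave the same fitted slope on one set of simulated errors.

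**Mediation.** The treatment-to-mediator path, with columns 1, time, treated, has rank 2 of 3, because treated and time are the same column. The mediator-to-outcome path is an association between two changes in the same people. It contains any mediated effect together with shared recovery and any common cause.

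**Scan order.** With visit indicators v1 (immediate) and v2 (one month), nominal order is 1 + v1 + 2·v2, an exact combination of columns already in the model.

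| Coding and attendance | Three visits | Pre and one month |
|---|---|---|
| Nominal visit | 3 of 4 | 2 of 3 |
| Attended session number, nothing missing | 3 of 4 | 2 of 3 |
| Session number, 6 drop out before one month | 3 of 4 | 2 of 3 |
| Session number, 6 attended immediate scans unusable | 3 of 4 | 2 of 3 |
| Session number, 1, 4 or 6 miss the immediate scan and return | 4 of 4 | 3 of 3 |

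The 6 is 20% of 30, the SAP's missing-data allowance, and the two middle cases are the causes it names (dropout and unusable imaging). A carryover indicator equal to 1 at both post-treatment scans, added to the three-visit model, also gives rank 3 of 4.

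**Illustration of how the labels could mislead.** This part rests on assumed correlations that are not in the documents. Take n = 24 (30 × 0.8), equal standard deviations before and after, no variation in treatment effect, and test-retest correlation r. Baseline score then correlates with change at −√((1 − r)/2):

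- r = 0.5: −0.50, significant at 0.05 in 73% of simulations
- r = 0.7: −0.39, 48%
- r = 0.9: −0.22, 18%

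A purely prognostic covariate correlated 0.3 or 0.5 with change is flagged in 29% or 72%.

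**The case against.** **The analyses are already hedged.** The SAP speaks of exploring and of potential moderators and mediators. No alpha, power or decision rests on them, and for secondary aims it puts magnitude ahead of significance. This stands, and it limits severity. It does not supply identification: exploratory status concerns certainty and multiplicity, not what quantity is being estimated.

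**Pre versus post can serve as the treatment contrast.** The SAP takes this route for its primary analyses, "treating the contrast (baseline versus post) as one univariate outcome". It is legitimate if untreated change is nil or at least unrelated to the baseline variable. Mediation needs a corresponding assumption for mediator and outcome, and no confounding between them. None of this is stated.

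**Design features limit untreated change.** The protocol requires MADRS to differ by less than 30% between screening and baseline, score thresholds at both visits, and at least moderate treatment refractoriness. These make large spontaneous change and strong regression to the mean less plausible, and the simulation above does not model them. They do not identify moderation.

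**Order can vary in practice.** The SAP admits participants with two of three scans, and Protocol 2a allows 3 to 6 scans. A reader might infer that the order term can never be estimated. That is too strong: coded as attended session number it can be, through those who miss the immediate scan and return or who have extra scans. It then reflects who attended irregularly and still does not isolate carryover. If software simply drops the aliased column, the visit contrasts do not change.

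**Some wording suggests a masked or multi-group design.** The protocol refers to an active group (2a, Motor threshold) and a blinded week (6k), and the SAP to a mask (Interim Analyses). No second arm, sham or randomisation is described, so the point rests on the single-arm design that is described.

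**Conclusion.** The point holds, and it is modest. In this design the moderator analysis estimates how baseline variables predict change, and the mediator analysis estimates how changes go together. Reading either as treatment moderation or mediation needs assumptions that the SAP does not state. The order term is fully aliased with time if coded as visit, depends on irregular attendance if coded as session number, and separates carryover from time under neither coding.

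The rank results depend only on one arm and one scan sequence. The false-flag percentages depend on assumed correlations and only illustrate the risk.

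A reader might infer that these models cannot be fitted, or that the primary result is invalid. The documents support neither. The time-by-baseline model has full rank, and the within-subject MADRS test is unaffected. The SAP's clinical objective, "To determine the effect of active, accelerated theta-burst stimulation over the left DLPFC on decreasing depressive symptoms", does rest on an assumption about untreated change when read causally, but that is a matter of interpretation and not a fault in the test. Nor do the documents show that any particular predictor would be spurious.

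**What to change.** Edit the two paragraphs of SAP section 9 on moderators and mediators and on missing data:

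1. Report the moderator analysis as exploratory baseline predictors of MADRS change, adjusted for baseline MADRS except where baseline MADRS is itself the candidate, with no claim of treatment moderation. Use the primary MADRS time point once it is reconciled: Protocol 2a (Outcome measures) sets it at immediate post-stimulation, while SAP Data Analyses sets it at one month.
2. Report the mediator analysis as exploratory associations between change in each candidate mediator (connectivity or any other measured) and MADRS change. If causal mediation is kept, state its untestable assumptions about untreated change in mediator and outcome and about the absence of mediator-outcome confounding, and make no claim of established mediation.
3. Delete the sentence on order and carryover, keep visit as the only time term, and state that order and carryover cannot be separated from time in this design.

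The cost is a few sentences and one covariate in the exploratory predictor models. No new data are needed, and these edits leave the primary test and sample size alone. The sponsor gives up only claims that the design cannot support.
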